## PRÉCIS

### Study Title

APPROACHES: Aligning Patient Preferences – a Role Offering Alzheimer’s patients, Caregivers, and Healthcare providers Education and Support

### Objectives

APPROACHES is a pragmatic cluster randomized control trial testing the impact of a structured ACP specialist program on patients with Alzheimer’s and dementia related diseases in nursing homes.

#### 1.1 Primary Objective R33 Phase (42 months)

1.1.1 Aim 1: Compare hospital transfers (admissions and emergency department visits) over 12 months between ADRD patients in intervention vs. control nursing homes

1.2.1.1 H1: Transfers will be lower among ADRD patients in intervention vs. control nursing homes.

#### 1.2 Secondary Objective

1.2.1 Aim 2: Compare the following secondary outcomes between ADRD patients in intervention vs. control nursing homes over 12 months: 1) hospice enrollment; and 2) death in hospital.

1.2.2.1 H1: ADRD patients in the intervention vs. control nursing homes will have:

1.2.2.1.1 i. Greater hospice enrollment;

1.2.2.1.2 and ii. Lower rates of dying in the hospital.

### Design and Outcomes

In intervention nursing homes, a nursing home provider (e.g. social worker or chaplain) will be trained as an ACP Specialist who will work with nursing home leaders to: i. Consolidate nursing home ACP procedures; ii. Train and educate staff; and iii. Facilitate ACP with patients and their family caregivers. Control nursing homes will apply the usual ACP practices. The implementation period will be 18 months. All ADRD patients in the nursing homes during the implementation will be followed for 12 months.

### Sample Size and Population

A total of 142 nursing homes will be randomized to either an intervention or control arm within each corporation (Signature, N= 109; Miller’s, N= 33).

## **1 STUDY OBJECTIVES**

### **1.1 Primary Objectives**

- 1.1.1 Aim 1: Compare hospital transfers (admissions and emergency department visits) over 12 months between ADRD patients in intervention vs. control nursing homes.
  - 1.2.1.1 H1: Transfers will be lower among ADRD patients in intervention vs. control nursing homes.

### **1.2 Secondary Objective**

- 1.2.1 Aim 2: Compare the following secondary outcomes between ADRD patients in intervention vs. control nursing homes over 12 months: 1) hospice enrollment and 2) death in hospital.
  - 1.2.2.1 H1: ADRD patients in the intervention vs. control nursing homes will have:
    - 1.2.2.1.1i. Greater hospice enrollment;
    - 1.2.2.1.2ii. Lower rates of dying in the hospital.

## **2 BACKGROUND AND RATIONALE**

### **2.1 Background on Condition, Disease, or Other Primary Study Focus**

A significant number of patients Alzheimer's disease or related dementia diagnoses will be cared for in nursing homes near the end of life. Unfortunately, many of these patients experience unwanted and burdensome medical treatments, such as potentially avoidable hospitalizations, that negatively impact quality of life. Advance care planning (ACP) discussions with patients and family caregivers are important to explore goals in advance of a crisis and support informed, values-based decision-making. The ACP process helps to ensure that preferences about treatments such as hospitalization are known, documented, and honored. Research indicates that ACP can reduce burdensome treatments and increase the likelihood that care will match documented preferences.

Nursing homes are currently required by regulations to offer ACP to patients and families. However, there are no training requirements for nursing home staff and approaches to fulfilling this regulatory and ethical responsibility vary widely, resulting in inconsistent ACP. The "Aligning Patient Preferences – a Role Offering Alzheimer's patients, Caregivers, and Healthcare providers Education and Support (APPROACHES)" trial will test the ACP Specialist Program. Existing nursing home staff members will be trained to enhance care and reduce unwanted, burdensome hospitalizations through improved ACP procedures, standardized staff education on ACP, and systematic ACP facilitation.

### **2.2 Study Rationale**

The ACP Specialist Training courses will serve as an educational tool to provide training to the ACP Specialists at enrolled nursing facilities that engage in ACP conversations. This tool will help refine and improve their knowledge of how to best have and record these conversations by providing tips, examples, and information on nursing homes.

A majority (72%) of nursing home patients have cognitive impairment and about half have a documented diagnosis of Alzheimer's Disease or a related dementia (ADRD). As a result of the progressive, downward trajectory of ADRD, 70% of patients live their final days in nursing homes. These patients often receive burdensome and expensive

treatments that may be avoidable and even unwanted. Hospitalizations are increasingly identified as a concern because of high burdens, high costs, and low clinical benefits in patients with advanced stages of dementia. Advance care planning (ACP) provides family caregivers of ADRD patients with education and support in identifying and documenting goals of care to align treatments with preferences. Documentation reflecting preferences for less aggressive treatment is associated with lower rates of hospitalization. However, nursing home staff are rarely trained to facilitate ACP or provided with strategies to integrate into practice resulting in highly variable practice and inaccurate documentation.

Under the auspices of a Centers for Medicare and Medicaid Services Initiative, our team has developed and successfully implemented a multi-component intervention to reduce avoidable hospitalizations of long-stay patients in 19 nursing homes across Indiana. While the scalability and sustainability of the full intervention model remains untested, our experience to date indicates the ACP component is particularly practical, effective, and translatable. The proposed ACP Specialist Program will build on this foundation by refining the ACP component to target ADRD patients and their family caregivers. This intervention will be delivered by existing nursing home staff (e.g., social worker).

The over-riding objective of this proposal is to conduct a pragmatic cluster randomized controlled trial (RCT) of “Aligning Patient Preferences – a Role Offering Alzheimer’s patients, Caregivers, and Healthcare providers Education and Support (APPROACHES)” that aims to improve ACP and goal-directed outcomes in nursing home patients with ADRD. In the R33 phase, we will conduct the full pragmatic RCT in partnership with 2 nursing home corporations (Signature HealthCARE and Miller’s Health Systems) in a combined total of 142 diverse facilities in 8 states. Consistent with the spirit of a pragmatic trial, we will use existing data sources including electronic health records (EHR), the Minimum Data Set 3.0 (MDS), and Medicare Claims data to characterize the cohort and measure outcomes. Hospital transfers over 12 months among ADRD patients is the 1° trial outcome.

### **3 STUDY DESIGN**

A total of 142 nursing homes will be randomized to either an intervention or control arm within each corporation (Signature, N= 109; Miller’s, N= 33). In intervention nursing homes, a nursing home provider (e.g. social worker) will be trained as an ACP Specialist who will work with nursing home leaders to: i. Consolidate nursing home ACP procedures; ii. Train and educate staff; and iii. Facilitate ACP with patients and their family caregivers. Control nursing homes will apply the usual ACP practices. The implementation period is expected to be 18 months. All ADRD patients in the nursing homes during the implementation will be followed for 12 months.

### **4 SELECTION AND ENROLLMENT OF PARTICIPANTS**

Facilities will be randomized to either the control arm or the intervention arm. This selection will take into account the choice of each organization considering half the organizations facilities are included in each arm.

The focus of the ACP Specialist will be patients with ADRD who reside in the nursing homes during the initiative, though other patients residing in the nursing home may benefit from it in keeping with the spirit of a pragmatic trial. Only patients with ADRD will be included in the analysis. ADRD is defined to include cognitive impairment or a documented diagnosis of dementia in the MDS. Patients will be excluded if they are currently enrolled in hospice at the start of the intervention period.

Eligible facilities who agree to participate in the trial will be stratified at two levels: corporate ownership (Signature HealthCARE and Miller's Health Systems) & average number of hospital transfers per 1000 person-days alive using 2017 MDS data provided by CMS. Facilities will be grouped into low versus high hospitalization rates, using the median rate for the nursing home system as the threshold value for dichotomization. Facilities will be randomized to the intervention or control within each strata at a 1-to-1 ratio. Specifically, randomization will occur at the facility level, meaning that all patients with ADRD in the intervention buildings are eligible for inclusion in the trial. Following random assignment, we will use all available facility and patient-level data to test the balance of the intervention and control arms.

Nursing home characteristics will be obtained from nursing home corporate partners and the MDS. Potentially eligible nursing homes will be reviewed by the Data Management and Analysis Workgroup in preparation for potential inclusion in the pragmatic cluster RCT. Problematic or unstable facilities will be removed in consultation with nursing home corporate leaders prior to randomization.

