#### **4.2 Exclusion Criteria**

- Patients currently enrolled in hospice at the start of the intervention period
- Problematic or unstable nursing homes
- Defined by corporate leadership prior to randomization

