## **6 STUDY PROCEDURES**

### **6.1 Description of Evaluations**

#### 6.1.1. Enrollment, Baseline, and/or Randomization

Nursing home Eligibility: All Medicare-certified nursing homes are eligible at Signature HealthCARE and Miller's Health Systems.

Nursing home Recruitment & Characteristics:

The ACP Specialist Program will be rolled out as a corporate initiative and nursing home Executive Directors will be requested to participate in the initiative by nursing home corporate leadership. It is anticipated all nursing home Executive Directors who are approached will agree to participate.

Nursing home corporate partners each provided data about key nursing home characteristics. At the time of randomization Signature HealthCARE owns 109 nursing homes in 8 states, with a total of 8,811 beds; 43% are rural. Miller's Health Systems owns 33 nursing homes, all in Indiana with 3,066 beds; 55% are rural. The mix of rural and urban facilities will provide a rich environment for this pragmatic trial. Self-reported 30-day hospital readmission rates for 2016 range from 13% for Miller's Health Systems and 17% for Signature HealthCARE nursing homes.

Random Assignment: Nursing homes will be sorted into groups that are comparable on hospital transfer rates. Eligible facilities who agree to participate in the trial will be stratified at two levels: corporate ownership (Signature HealthCARE and Miller's Health Systems) & average number of hospital transfers per 1000 person-days alive using 2017 MDS data. Facilities will be grouped into low versus high hospitalization rates, using the median rate for the nursing home system as the threshold value for dichotomization. Facilities will be randomized to the intervention or control within each strata at a 1-to-1 ratio. Specifically, randomization will occur at the facility level, meaning that all patients not currently on hospice at the start of the intervention period in the intervention buildings are eligible for inclusion in the trial. The intervention focuses on patients with ADRD, but other residents of intervention facilities are not excluded. Following random assignment, we will use all available facility and patient-level data to test the balance of the intervention and control arms.

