### **9.3 Interim analyses and Stopping Rules**

We will not be conducting an interim analysis or developing rules for stopping the trial early for several reasons. The planned intervention of a trained ACP Specialist who will augment usual care is unlikely to cause harm. The IRB has determined that this study is minimal risk. Particularly given the delay in obtaining Medicare claims for determining the primary outcome, hospitalization or emergency department visits, it will not be feasible to determine the differences in this outcome between the intervention and control groups until the end of the 12 month outcome observation period.

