because the analysis generates estimates of treatment effectiveness in a more realistic way. In fact, clinical effectiveness can be severely overestimated if ITT analysis is not performed. Within the ITT framework, we propose to analyze the trial data using appropriate generalized linear models. Specifically, we plan to compare the rates of hospital admissions in patients residing in the intervention vs control facilities. In line with intention-to-treat principles and our cluster randomized design, hospitalizations will be analyzed at the facility level, including for residents who moved across intervention and control buildings during the study period. Group assignment will be based on the facility each resident was first admitted to during the intervention period. Thus, some residents may have a documented ACP encounter in intervention facilities but also spent some time in control facilities. The analysis will be carried out using an appropriate count data regression model, length of observation will be adjusted as an offset parameter. We will test the levels of extra-Poisson variation to determine if a Poisson regression model is sufficient for the analysis. If the level of variation is beyond what can be accommodated by the Poisson model, we will consider using negative binomial regression. Similarly, we will test the presence of extra zeros that beyond the Poisson or negative binomial models. If necessary we will consider the use of zero-inflated Poisson or negative binomial regression analysis. Correlations among outcomes measured from residents in the same facility will be accounted for by adding random facility effects into the regression models. This analytical approach handles missing data (early dropout due to death or transfer to hospice) more easily because of the inclusion of offsetting parameters in the model.

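### The hospice exclusion is checked only at programme start, so later entrants already on hospice join the cohort and dilute the hospice comparison

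*Combined protocol and SAP*

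**What the plan says.** **The exclusion.** Section 4 states: "Patients will be excluded if they are currently enrolled in hospice at the start of the intervention period". Section 4.2 lists the same group: "Patients currently enrolled in hospice at the start of the intervention period". Section 6.1.1 puts it positively: "all patients not currently on hospice at the start of the intervention period in the intervention buildings are eligible for inclusion in the trial". All three use one time point.

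**The cohort.** Section 3 says "The implementation period is expected to be 18 months" and then "All ADRD patients in the nursing homes during the implementation will be followed for 12 months"; the Précis describes the same cohort. Section 9.5 sets the arm as follows: "Group assignment will be based on the facility each resident was first admitted to during the intervention period". This presupposes that some residents enter after the programme has begun.

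**The outcomes and model.** Section 9.4.2.1 names hospice enrollment over 12 months as a secondary outcome. It does not say from what date, or whether the election must be new. Section 9.5 uses observation time as the offset in the primary count model and says the approach "handles missing data (early dropout due to death or transfer to hospice) more easily because of the inclusion of offsetting parameters".

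**The window.** Section 9.3 says outcome differences cannot be determined "until the end of the 12 month outcome observation period", which reads more like one fixed window than a separate 12 months for each resident.

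**The concern.** The exclusion is worded for a closed cohort, and the cohort is described as open. Two residents in the same position on the day they come under observation are treated differently: the one on hospice at programme start is out, and the one admitted on hospice in month 3 is in. Nothing in the plan explains the difference.

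The hospice comparison is most exposed. A resident already on hospice at entry is not at risk of a new election, so the intervention cannot change that outcome for them. They stay in the denominator and pull the arms together. Their share could also differ by arm, because later entry follows randomization and facility staff are not described as blinded. For the primary outcome, the question is whether these residents have any usable person-time.

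**Working it through.** **1. Does any rule catch these residents?** Sections 4, 4.2 and 6.1.1 all look at programme start. No section checks hospice status at a resident's own entry or defines a resident-level time zero. If claims were searched back to programme start, the rule could catch a later entrant whose hospice stay was already running then. It cannot catch one who elected hospice between programme start and entry.

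**2. Effect on the hospice outcome.** Let h be the share of the analysed cohort on hospice at entry, equal in both arms, and let p0 and p1 be the 12-month risks of a new election among the rest. Assumptions: p0 = 0.20, p1 = 0.26, h = 0.03, 0.05 or 0.10. The documents give none of these.

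- If existing hospice counts as enrollment, risk = h + (1 − h)p.
- If only new elections count, risk = (1 − h)p.
- In both cases the difference is (1 − h)(p1 − p0).

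| h | Counted: control, intervention | Ratio | New only: control, intervention | Ratio | Difference (points) |
|---|---|---|---|---|---|
| 0 | 20.0%, 26.0% | 1.30 | 20.0%, 26.0% | 1.30 | 6.0 |
| 0.03 | 22.4%, 28.2% | 1.26 | 19.4%, 25.2% | 1.30 | 5.8 |
| 0.05 | 24.0%, 29.7% | 1.24 | 19.0%, 24.7% | 1.30 | 5.7 |
| 0.10 | 28.0%, 33.4% | 1.19 | 18.0%, 23.4% | 1.30 | 5.4 |

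The difference is diluted under either definition. The ratio is diluted only under the first.

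With 20% vs 25% instead, and existing hospice counted, the ratio falls from 1.25 to 1.20 at h = 0.05 and 1.16 at h = 0.10. The difference falls from 5.0 to 4.75 and 4.5 points.

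**3. Unequal shares by arm (illustration).** Assume no true effect, 20% new elections in both arms, and 5% of control and 8% of intervention residents on hospice at entry.

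- Counted: 0.05 + 0.95 × 0.20 = 24.0% vs 0.08 + 0.92 × 0.20 = 26.4%, a ratio of 1.10.
- New only: 0.95 × 0.20 = 19.0% vs 0.92 × 0.20 = 18.4%, a ratio of 0.97.

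Either way a difference appears that the intervention did not cause.

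**4. Primary power.** Section 9.2 gives 81% for 60 facilities per arm, 50 residents each, 1.0 vs 0.8 events per resident-year and alpha 0.05, with a between-facility CV stated only as below 0.5. Taking y = 50 resident-years per facility and a two-sided test:

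power = Φ( √[ 60 × 0.2² / {1.8/y + CV² × (1.0² + 0.8²)} ] − 1.96 )

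- CV = 0.50: √(2.4 / 0.446) − 1.96 = 0.36, power 64%.
- CV = 0.40: √(2.4 / 0.2984) − 1.96 = 0.88, power 80.9%.

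The 81% is therefore reproduced at a CV of about 0.40, which agrees with the stated bound; the value actually used is not given. Holding the CV that gives 81.0% and removing person-time, power is 80.5% at y = 45, 79.8% at y = 40 and 77.9% at y = 30. Between-facility variation dominates, so even a 20% loss of person-time costs little more than one point.

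**The case against.** **The outcome may mean new elections only.** A reader might infer that later entrants on hospice are counted as events at time zero. Section 9.4.2.1 does not say so, and enrollment over 12 months is naturally read as a new election. This objection stands against the fall in the ratio. It does not remove the loss in the risk difference, because these residents remain in the denominator.

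**The primary model need not fail.** A reader might infer that these residents have zero observation time, so that the log offset is undefined. Section 9.5 mentions transfer to hospice as early dropout in a parenthesis but states no censoring rule, and someone admitted on hospice has not transferred during follow-up. If hospice does not end observation, they contribute ordinary person-time. If it does, they may contribute little or none. In either case they can contribute to death in hospital.

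**The entry window is not certain.** Section 9.3 can be read as one fixed 12-month window. If a closed cohort was intended, sections 3 and 9.5 need correcting; if an open one, the exclusion does. One of them must change. Reading programme start as each resident's own start does not help, since section 9.5 uses the intervention period as a programme-wide interval.

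**The purpose is not given.** It is tempting to say that the exclusion exists to remove residents who already have the secondary outcome. No section gives a rationale, and the point does not depend on one.

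**The size is modest and assumed.** This stands. The share h refers to the whole cohort, while only later entrants are affected. If half the cohort were later entrants (an assumption), h = 0.10 would need 0.10 / 0.50 = 20% of them to arrive on hospice, and h = 0.03 would need 6%.

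**Conclusion.** The point holds for the exclusion rule itself. Followed as written, it removes residents on hospice at programme start and admits later entrants already on hospice, and no other section corrects this. The hospice risk difference shrinks by the factor (1 − h): from 6.0 to between 5.8 and 5.4 points at assumed rates of 20% vs 26% and h of 3% to 10%. The fall in the ratio, from 1.30 to between 1.26 and 1.19, is conditional on existing hospice being counted as enrollment.

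The documents do not support saying that these residents are counted as hospice events, that they have no follow-up, or that the primary model breaks down. The consequence for primary power is small. The change is worth making because it is cheap and removes an inconsistency in a named secondary comparison.

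**What to change.** - **Sections 4, 4.2 and 6.1.1:** define each resident's index date as programme start for those present then, and otherwise the first entry during the intervention period. Exclude residents enrolled in hospice on that date, by the same rule in both arms, using MDS and claims records.
- **Section 9.4.2.1:** define hospice enrollment as a new election after the index date.
- **Section 9.5:** state whether a hospice election ends observation for the primary outcome.
- **Sections 3 and 9.3:** reconcile the single 12-month observation window with the 18-month implementation and the entry of residents during it.
- **Reporting:** give the number excluded for hospice at the index date by arm, because for later entrants this exclusion is applied after randomization and could differ between arms.

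The cost is wording in these sections and a small change to the cohort code. MDS and claims are already planned sources. The analysed cohort becomes slightly smaller.

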### **9.4 Outcomes**

#### **9.4.1 Primary outcome**

9.4.1.1 Hospital transfers over 12 months among ADRD patients

#### **9.4.2 Secondary outcomes**

9.4.2.1 Hospice enrollment over 12 months among ADRD patients

9.4.2.2 Death in hospital over 12 months among ADRD patients

### **9.5 Data Analyses**

Design consideration. The R33 phase of the study has two aims: (Aim 1 – Primary) To compare hospital transfers (admissions and emergency department visits) over 12 months between ADRD patients in the intervention and control facilities; and (Aim 2 - Secondary) assess the interventional effect of the ACP Specialist Program on hospice enrollment and place of death. Towards these ends, we employ a cluster RCT design. With this design, randomization will be carried out at the nursing home level, stratified by nursing home corporate ownership and baseline hospitalization transfer rates (low versus high). All patients at a given nursing home will have the same intervention assignment. The trial outcomes will be analyzed at the individual patient level and reported at the facility level. The cluster RCT with nursing home randomization is chosen because of its ability to simultaneously maximize the implementational feasibility and minimize the contamination risk. Counts of hospital transfers and emergency department visits incurred by individual ADRD patients during the follow-up period will be considered as the primary outcome. We designed the trial to ensure adequate power for the hypothesis concerning the primary outcome. Average age and proportion of female patients is similar across our nursing home partner facilities and the U.S. The % of Black patients ranges from 6-17% across the population of our partner nursing homes. About half of nursing home patients have a dementia diagnosis. This is similar for our partner facilities.

Analysis will be carried out in an intention-to-treat (ITT) framework, which gives a pragmatic estimate of the interventional benefit. The ITT analysis will use data from all eligible patients in randomized facilities, regardless of the level of facilities' adherence to the study protocol and patient attrition. ITT is a preferred approach for pragmatic trials

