The nursing home staff member designated as the ACP Specialist will complete a longer training (approximately 7 hours) and will receive a hard-copy manual including sample, educational handouts and access to videos for patients, families, and other nursing home staff, documentation instructions, tracking tools, and tips for navigating common barriers. Due to the COVID-19 pandemic and its significant impact on NHs, an Introductory Launch Course was created for ACP Specialists to complete prior to implementation at their facility with the understanding that all additional training modules would then be completed. The training will include specific information about decision-making for patients with dementia. Training materials are anticipated to include OPTIMISTIC educational tools created by [name] and materials developed by [name]. Core expectations include review and modification of ACP procedures as needed, education provided to other nursing home staff, and dedicated time to coordinate and facilitate ACP discussions with ADRD patients and/or family caregivers using the target assignment list. Based on experience with OPTIMISTIC, the ACP Specialist will require a minimum of 1 day per week (20% FTE) initially, with a reduction over time after the initial start-up work. Dedicated time and schedule flexibility are critical to the success of the ACP Specialist to reach family caregivers and facilitate conversations.

Consistent with the principles of a pragmatic trial, instructions about how to implement the protocol role will be highly flexible. For example, some facilities may decide to train more than one ACP Specialist within the building to share responsibilities. There is also flexibility in level of expertise required by practitioners delivering the intervention so the ACP Specialist may be any staff person deemed qualified by the nursing home Executive Director to fulfill the role, though it is anticipated it will likely be a social worker or a nurse. It is expected that there will be adaptations to the ACP tools and educational materials as needed.

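### The only pre-intervention transfer rate named is a dichotomised 2017 MDS stratifier; a recent continuous facility rate in the primary model would add precision at little cost

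*Combined protocol and SAP*

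**What the plan says.** Section 4 forms randomization strata from corporate ownership and the facility's "average number of hospital transfers per 1000 person-days alive using 2017 MDS data provided by CMS". Homes are classed as low or high "using the median rate for the nursing home system as the threshold value for dichotomization". Section 6.1.1 repeats this, and section 9.5 calls the low/high factor the baseline rate. Neither section 4 nor section 6.1.1 says that the 2017 rate was restricted to residents with ADRD, whereas only patients with ADRD enter the analysis. The other historical figure, in section 6.1.1, is a self-reported 30-day readmission rate for 2016, which is a different measure.

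On timing, section 13 states: "Due to the COVID-19 pandemic and its significant impact on NHs, an Introductory Launch Course was created". Specialists were to complete that course before implementation at their home. No launch or randomization date is printed.

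On source, section 9.3 refers to the "delay in obtaining Medicare claims for determining the primary outcome, hospitalization or emergency department visits". Section 2.2 is broader and lists electronic health records together with "the Minimum Data Set 3.0 (MDS), and Medicare Claims data to characterize the cohort and measure outcomes"; section 9.1 repeats that list.

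On use after randomization, section 4 promises that "we will use all available facility and patient-level data to test the balance of the intervention and control arms" but names no variable, window or source. Section 9.2 expects covariate adjustment to raise power and names no covariate. The primary count model in section 9.5 has a length-of-observation offset and random facility effects. It names no baseline rate and no stratum term.

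**The concern.** In a cluster trial with about 50 residents per home, precision depends mostly on how much homes differ from one another. A home's own earlier transfer rate is an obvious covariate for explaining that difference. The plan has such a rate in only one form. It is from 2017, is reduced to two classes, and is separated from the trial by a disruption that the protocol itself calls significant. The plan does not show that it was built in the same way as the endpoint, and it does not enter the model as written.

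Two things are at stake: the width of the confidence interval for the primary comparison, and whether readers can see how similar the arms' transfer rates were shortly before launch. The balance check could include a recent rate, but nothing commits it to do so.

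**Working it through.** **Inputs from section 9.2.** 60 homes per arm (c); 50 residents per home, taken as y = 50 resident-years; rates λ0 = 1.0 and λ1 = 0.8 per resident-year; alpha 0.05, taken as two-sided; between-home CV (k) stated only as below 0.5; power 81%. Section 3 randomizes 142 homes, or 142/2 = 71 per arm. Section 9.2 is framed in hospitalizations, so carrying these figures over to all transfers is illustrative.

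**Formula (Hayes-Bennett, rates).** V = (λ0+λ1)/y + k²(λ0²+λ1²); z = √[(c−1)(λ0−λ1)²/V]; power = Φ(z − 1.96).

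**The plan's figure.**
- k = 0.40: V = 0.036 + 0.16 × 1.64 = 0.298; z = √(59 × 0.04/0.298) = 2.81; power 80.3%.
- k = 0.50: V = 0.036 + 0.25 × 1.64 = 0.446; z = 2.30; power 63.3%.

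The stated 81% therefore fits a CV of about 0.40, which the stated bound allows. The exact CV is not given, so this is not an error.

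**Share of variance that lies between homes.** At k = 0.40: 0.262/0.298 = 88%. At k = 0.50: 0.410/0.446 = 92%.

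**Effect of a facility baseline.** Let r be the correlation between the baseline facility rate and the home's trial-period rate. The documents give no value, so r is an assumption throughout. A continuous covariate leaves k²(1−r²). A median split explains only r² × 2/π of the between-home variance (normal approximation).

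Power with a continuous baseline:

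| | no baseline | r = 0.5 | r = 0.6 | r = 0.7 |
|---|---|---|---|---|
| k = 0.40, 60 per arm | 80.3% | 89.0% | 92.5% | 96.1% |
| k = 0.40, 71 per arm | 86.5% | 93.4% | 96.0% | 98.2% |
| k = 0.50, 60 per arm | 63.3% | 74.6% | 80.3% | 87.3% |
| k = 0.50, 71 per arm | 70.7% | 81.5% | 86.5% | 92.2% |

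Example, k = 0.40, 60 per arm, r = 0.5: residual k² = 0.16 × 0.75 = 0.12; V = 0.036 + 0.12 × 1.64 = 0.233; z = 3.18; power 89.0%.

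Power with a median split in the model (k = 0.40, 60 per arm): 82.3% at r = 0.3 and 85.8% at r = 0.5. The split explains 6% and 16% of between-home variance respectively.

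**Chance imbalance.** If the 2017 stratum said nothing about rates at launch (the extreme case), the 95% range for the difference in mean facility rates with 71 per arm would be 1.96 × k × √(2/71): ±13% at k = 0.40 and ±16% at k = 0.50, against a 20% target effect. If the stratum has r = 0.5, the ranges are ±12% and ±15%. This is ordinary random variation that the confidence interval already covers. A good baseline covariate would narrow it.

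**The case against.** The strongest reply is that the 2017 rate is used only to form strata and is never offered as evidence that the homes were alike at launch. Comparability rests on 1:1 randomization of 142 homes. That stands. A reader might infer that an old stratifier leaves the arms non-comparable or the effect estimate biased; the documents do not support this. An uninformative stratifier costs precision and nothing else.

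A reader might also infer that the baseline and the outcome come from different sources. Section 9.3 points that way, but sections 2.2 and 9.1 list the MDS among the data used to measure outcomes, and section 13 plans to check MDS and claims records against the health record. The most that can be said is that a common source and definition are not shown.

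Third, the plan already intends covariate adjustment (section 9.2) and a broad balance check (section 4). Both statements could accommodate a recent rate, but neither names one.

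Fourth, the gain depends on assumed correlations. If the 2017 rate, entered as a continuous covariate, had r = 0.5 and a recent one r = 0.6, the comparison at k = 0.40 with 60 per arm would be 89% against 92.5%, a small difference. A pre-launch year affected by the pandemic may not predict the trial period better than 2017 does. This also stands, and it is why the size of the benefit is left as a range.

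Finally, with 71 homes per arm and a CV of 0.40, power exceeds 80% without any change, so the point does not show an underpowered trial.

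**Conclusion.** The point holds as an inexpensive gain in precision that the plan forgoes. It is not a flaw in the validity of the comparison. The documents establish that the one pre-intervention transfer rate named is from 2017, is dichotomised and predates COVID-19, that its match to the endpoint's source, definition and ADRD population is not shown, and that section 9.5 names no baseline rate or stratum term.

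Relative to the model as written, a continuous baseline with r between 0.5 and 0.7 would raise power by roughly 9 to 16 percentage points at CV 0.40 with 60 homes per arm, and by roughly 7 to 12 points with 71. If the CV is nearer the stated bound of 0.5, the gain is larger. All of this rests on the assumed r, a two-sided test, y = 50 resident-years per home and a normal approximation. The increment over a model that already holds the 2017 stratum would be smaller.

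**What to change.** Leave the randomization strata unchanged. In section 9.5, specify that the primary count model includes corporation, the 2017 low/high stratum and, in addition to these, a continuous facility-level transfer rate among ADRD residents over a 12-month window before launch. The new rate should supplement the 2017 stratum, because the randomization was stratified on that factor.

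Define the rate with the same sources, event definition and eligibility rules as the primary outcome. Use one fixed calendar window for both arms, for example anchored on a corporation-level start date, because control homes have no launch date of their own. In section 4, name the same rate as an entry in the balance table. Fix the specification before any arm-level outcomes are seen.

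The cost is one additional pre-launch year in the CMS data request that the trial already makes, plus the SAP wording. Residents are not contacted and no home is re-randomized. The downside is that the extra year may turn out to predict the trial period poorly, in which case little precision is gained.
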